### 6.3 Outcome variables and study follow-up:

#### 6.3.1 Outcome variables

Primary Effectiveness outcomes of interest: (definitions provided in **Appendix A**):

- **Primary Outcome:** VTE and cause-specific mortality
- **Secondary Outcome:** Individual components
  - Hospital admission for VTE (principal diagnosis position)
  - Cause-specific mortality
    - Inpatient mortality identified using discharge status codes from hospitalization for VTE

Safety outcome of interest:

1. Major bleeding

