| • Acute symptomatic proximal deep vein thrombosis (DVT) with evidence of proximal thrombosis that involves at least the popliteal vein or a more proximal vein, demonstrated by imaging with: - compression ultrasound (CUS), including grey-scale or color-coded Doppler, OR - ascending contrast venography                                                                                                                                                                                        | Measured 180 days prior to and including day of drug initiation in any diagnosis position and in an inpatient or ED care setting

Deep vein thrombosis (DVT):
ICD-9 Dx: 451.xx, 453.xx
ICD-10 Dx: I26.xx, I80.xx, I81.xx, I82.xx, I26.xx |                                                                                                                                                                                                                                                                                  |                                                                                                                                                                                                                                                                                                                                                                                                                                                                                                                    |

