| 453.2                                      | EMBOLISM AND THROMBOSIS OF INFERIOR VENA CAVA                                         |
| 453.4                                      | ACUTE VENOUS EMBOLISM AND THROMBOSIS OF DEEP VESSELS OF LOWER EXTREMITY               |
| 453.4                                      | ACUTE VENOUS EMBOLISM AND THROMBOSIS OF UNSPECIFIED DEEP VESSELS OF LOWER EXTREMITY   |
| 453.41                                     | ACUTE VENOUS EMBOLISM AND THROMBOSIS OF DEEP VESSELS OF PROXIMAL LOWER EXTREMITY      |
| 453.42                                     | ACUTE VENOUS EMBOLISM AND THROMBOSIS OF DEEP VESSELS OF DISTAL LOWER EXTREMITY        |
| 453.5                                      | CHRONIC VENOUS EMBOLISM AND THROMBOSIS OF DEEP VESSELS OF LOWER EXTREMITY             |
| 453.5                                      | CHRONIC VENOUS EMBOLISM AND THROMBOSIS OF UNSPECIFIED DEEP VESSELS OF LOWER EXTREMITY |
| 453.51                                     | CHRONIC VENOUS EMBOLISM AND THROMBOSIS OF DEEP VESSELS OF PROXIMAL LOWER EXTREMITY    |
| 453.52                                     | CHRONIC VENOUS EMBOLISM AND THROMBOSIS OF DEEP VESSELS OF DISTAL LOWER EXTREMITY      |
| 453.8                                      | ACUTE VENOUS EMBOLISM AND THROMBOSIS OF OTHER SPECIFIED VEINS                         |
| 453.82                                     | ACUTE VENOUS EMBOLISM AND THROMBOSIS OF DEEP VEINS OF UPPER EXTREMITY                 |
| 453.83                                     | ACUTE VENOUS EMBOLISM AND THROMBOSIS OF UPPER EXTREMITY UNSPECIFIED                   |
| 453.84                                     | ACUTE VENOUS EMBOLISM AND THROMBOSIS OF AXILLARY VEINS                                |
| 453.85                                     | ACUTE VENOUS EMBOLISM AND THROMBOSIS OF SUBCLAVIAN VEINS                              |
| 453.86                                     | ACUTE VENOUS EMBOLISM AND THROMBOSIS OF INTERNAL JUGULAR VEINS                        |
| 453.87                                     | ACUTE VENOUS EMBOLISM AND THROMBOSIS OF OTHER THORACIC VEINS                          |
| 453.89                                     | ACUTE VENOUS EMBOLISM AND THROMBOSIS OF OTHER SPECIFIED VEINS                         |

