# Appendix A

|                                             |                                                                                            |
|---------------------------------------------|--------------------------------------------------------------------------------------------|
| 453.9                                       | EMBOLISM AND THROMBOSIS OF UNSPECIFIED SITE                                                |
| ICD-10 Dx inpatient primary position |                                                                                            |
| PE                                   |                                                                                            |
| I26.0                                       | Pulmonary embolism with acute cor pulmonale                                                |
| I26.01                                      | Septic pulmonary embolism with acute cor pulmonale                                         |
| I26.02                                      | Saddle embolus of pulmonary artery with acute cor pulmonale                                |
| I26.09                                      | Other pulmonary embolism with acute cor pulmonale                                          |
| I26.9                                       | Pulmonary embolism without acute cor pulmonale                                             |
| I26.99                                      | Other pulmonary embolism without acute cor pulmonale                                       |
| DVT                                  |                                                                                            |
| I80.1                                       | Phlebitis and thrombophlebitis of femoral vein                                             |
| I80.10                                      | Phlebitis and thrombophlebitis of unspecified femoral vein                                 |
| I80.11                                      | Phlebitis and thrombophlebitis of right femoral vein                                       |
| I80.12                                      | Phlebitis and thrombophlebitis of left femoral vein                                        |
| I80.13                                      | Phlebitis and thrombophlebitis of femoral vein, bilateral                                  |

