## Appendix A

|         |                                                                                        |
|---------|----------------------------------------------------------------------------------------|
| I80.232 | Phlebitis and thrombophlebitis of left tibial vein                                     |
| I80.233 | Phlebitis and thrombophlebitis of tibial vein, bilateral                               |
| I80.239 | Phlebitis and thrombophlebitis of unspecified tibial vein                              |
| I80.29  | Phlebitis and thrombophlebitis of other deep vessels of lower extremities              |
| I80.291 | Phlebitis and thrombophlebitis of other deep vessels of right lower extremity          |
| I80.292 | Phlebitis and thrombophlebitis of other deep vessels of left lower extremity           |
| I80.293 | Phlebitis and thrombophlebitis of other deep vessels of lower extremity, bilateral     |
| I80.299 | Phlebitis and thrombophlebitis of other deep vessels of unspecified lower extremity    |
| I80.3   | Phlebitis and thrombophlebitis of lower extremities, unspecified                       |
| I80.9   | Phlebitis and thrombophlebitis of unspecified site                                     |
| I82.0   | Budd-Chiari syndrome                                                                   |
| I82.1   | Thrombophlebitis migrans                                                               |
| I80.3   | Phlebitis and thrombophlebitis of lower extremities, unspecified                       |
| I82.4   | Acute embolism and thrombosis of deep veins of lower extremity                         |
| I82.40  | Acute embolism and thrombosis of unspecified deep veins of lower extremity             |
| I82.401 | Acute embolism and thrombosis of unspecified deep veins of right lower extremity       |
| I82.402 | Acute embolism and thrombosis of unspecified deep veins of left lower extremity        |
| I82.403 | Acute embolism and thrombosis of unspecified deep veins of lower extremity, bilateral  |
| I82.409 | Acute embolism and thrombosis of unspecified deep veins of unspecified lower extremity |
| I82.41  | Acute embolism and thrombosis of femoral vein                                          |
| I82.411 | Acute embolism and thrombosis of right femoral vein                                    |
| I82.412 | Acute embolism and thrombosis of left femoral vein                                     |

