## Appendix A

|         |                                                                            |
|---------|----------------------------------------------------------------------------|
| I82.629 | Acute embolism and thrombosis of deep veins of unspecified upper extremity |
| I82.890 | Acute embolism and thrombosis of other specified veins                     |
| I82.90  | Acute embolism and thrombosis of unspecified vein                          |
| I82.A1  | Acute embolism and thrombosis of axillary vein                             |
| I82.A11 | Acute embolism and thrombosis of right axillary vein                       |
| I82.A12 | Acute embolism and thrombosis of left axillary vein                        |
| I82.A13 | Acute embolism and thrombosis of axillary vein, bilateral                  |
| I82.A19 | Acute embolism and thrombosis of unspecified axillary vein                 |
| I82.B1  | Acute embolism and thrombosis of subclavian vein                           |
| I82.B11 | Acute embolism and thrombosis of right subclavian vein                     |
| I82.B12 | Acute embolism and thrombosis of left subclavian vein                      |
| I82.B13 | Acute embolism and thrombosis of subclavian vein, bilateral                |
| I82.B19 | Acute embolism and thrombosis of unspecified subclavian vein               |
| I82.C1  | Acute embolism and thrombosis of internal jugular vein                     |
| I82.C11 | Acute embolism and thrombosis of right internal jugular vein               |
| I82.C12 | Acute embolism and thrombosis of left internal jugular vein                |
| I82.C13 | Acute embolism and thrombosis of internal jugular vein, bilateral          |
| I82.C19 | Acute embolism and thrombosis of unspecified internal jugular vein         |

[figure not shown]
[figure not shown]

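### The printed ICD-9 and ICD-10 primary-outcome lists are not equivalent: vena cava and other thoracic vein thrombosis count under ICD-9 only

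*Combined protocol and SAP*

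**What the plan says.** Section 6.3.1 defines the VTE component of the primary outcome as a hospital admission with VTE as principal diagnosis. Appendix A has a VTE sheet with two written-out code lists, one for each coding system.

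- **ICD-9 list, DVT block.** After Budd-Chiari and migrans it carries 453.2, "EMBOLISM AND THROMBOSIS OF INFERIOR VENA CAVA", then the leg-vein codes. Further down it has arm, axillary, subclavian and jugular codes, then 453.87 for the remaining thoracic veins, then 453.89, a residual code labelled "ACUTE VENOUS EMBOLISM AND THROMBOSIS OF OTHER SPECIFIED VEINS".
- **ICD-10 list.** This has its own heading, "ICD-10 Dx inpatient primary position". Its DVT block goes from I82.0 (Budd-Chiari) to I82.1, "Thrombophlebitis migrans", then to a second copy of I80.3, then to I82.4, "Acute embolism and thrombosis of deep veins of lower extremity". It continues through I82.5, I82.6, I82.890 ("Acute embolism and thrombosis of other specified veins"), I82.90, I82.A1, I82.B1 and I82.C1.
- **Cohort entry.** The DVT inclusion criterion uses whole code families: "ICD-10 Dx: I26.xx, I80.xx, I81.xx, I82.xx, I26.xx".

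Appendix A also says that ICD-9 codes were converted by forward and backward mapping, and that full ICD-10 lists are held in an external folder.

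**The concern.** The study windows appear to span both coding systems, so the two lists should describe the same event. As printed they do not: two sites count as recurrent VTE in one period and drop out in the other. The vena cava is a deep and proximal site. The ICD-10 list nevertheless keeps distal, chronic and arm-vein codes and does not name the vena cava. No reason for dropping either site is given.

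What is at stake is a primary outcome whose definition depends on calendar time. The matched covariate table in Appendix B shows no calendar-time variable, so that table gives no assurance that the two arms are spread alike over the coding periods.

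**Working it through.** **1. Row-by-row comparison of the DVT sites**

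| Site | ICD-9 row | ICD-10 row |
|---|---|---|
| Budd-Chiari | 453 | I82.0 |
| Migrans | 453.1 | I82.1 |
| Inferior vena cava | 453.2 | none; a repeated I80.3 stands here |
| Leg, acute | 453.4, 453.41, 453.42 | I82.4 and subcodes |
| Leg, chronic | 453.5, 453.51, 453.52 | I82.5 and subcodes |
| Arm | 453.82, 453.83 | I82.6, I82.60, I82.62 and subcodes |
| Axillary, subclavian, jugular | 453.84, 453.85, 453.86 | I82.A1, I82.B1, I82.C1 |
| Remaining thoracic veins | 453.87 | none |
| Residual category | 453.89 | I82.890 |

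No ICD-10 label contains the words vena cava or thoracic, and the numbering jumps from I82.1 to I82.4. The residual row I82.890 does not clearly fill the gap: its ICD-9 counterpart, 453.89, is listed separately from 453.2 and 453.87.

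**2. Share of each calendar window under ICD-10**

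The windows come from Section 5.2.1; all start on 21 August 2014. The change date of 1 October 2015 is my assumption. It puts 406 days of each window under ICD-9. Share = (window days − 406) / window days.

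- Medicare, to 31 December 2017: (1,229 − 406) / 1,229 = 823 / 1,229 = 67.0%.
- MarketScan, to 31 December 2018: (1,594 − 406) / 1,594 = 1,188 / 1,594 = 74.5%.
- Optum, to 31 March 2020: (2,050 − 406) / 2,050 = 1,644 / 2,050 = 80.2%.
- Weighted by matched patients: (3,398 × 0.670 + 2,762 × 0.745 + 980 × 0.802) / 7,140 = 71.7%.

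ICD-10 covers the larger part of all three windows for any change date before 26 April 2016, the midpoint of the shortest window. These are shares of calendar time. The documents do not give person-time by year.

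**3. The plan's own power figure**

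Expected events (Sections 9 and 10): 7,140 × 13.74 / 1,000 = 98.1036. With a hazard ratio of 0.84, a margin of 1.8, two-sided alpha 0.05 and 1:1 matching, the Schoenfeld formula gives

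power = Φ( (√98.1036 / 2) × ln(1.8 / 0.84) − 1.960 ) = Φ(4.952 × 0.762 − 1.960) = Φ(1.814) = 0.9652.

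This matches the stated 0.965194245. The three database-specific values (0.2731, 0.6311, 0.7672) also reproduce.

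**4. Possible effect of restoring the missing codes**

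Let s be the share of all outcome events whose only qualifying principal diagnosis is at a missing site, and e the ICD-10 share of follow-up. If the printed list was the one run, the aligned count is 98.1036 / (1 − s × e). The documents give no value for s, so I assume 0.5% to 10%, with e from 0.67 to 0.80.

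- s = 0.005, e = 0.67: 98.1036 / 0.99665 = 98.4 events, power 0.9657.
- s = 0.02, e = 0.75: 98.1036 / 0.985 = 99.6 events, power 0.9673.
- s = 0.10, e = 0.80: 98.1036 / 0.92 = 106.6 events, power 0.9759.

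**5. Reach of the entry definition**

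In the matched table of Appendix B, 3,563 warfarin and 3,566 apixaban patients have a PE code: 7,129 of 7,140, or 99.8%. At most 11 patients lack one.

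**The case against.** The strongest reply is that the list actually run cannot be seen. Appendix A sends the reader to an external folder for full ICD-10 lists and missing information. Elsewhere it prints ICD-9 codes only, for example for ischemic stroke and anemia. A fuller list may therefore have been used. This stands as a limit on certainty. It does not remove the point, because the VTE sheet does write out its ICD-10 codes at length, and a reader following it would apply the narrower definition.

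A reader might also infer four stronger things that the documents do not support.

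- **That the omission erodes the stated power.** The 98.1 events rest on the reported risk of 13.74 per 1,000. If the printed list was run, the omission is already inside that figure. If a fuller list was run, there is no omission. Either way nothing further is lost, and adding codes can only add events.
- **That all vena cava recurrences are missed.** An admission with PE, iliac or femoral thrombosis as principal diagnosis is still counted.
- **That patients commonly enter on a vena cava thrombosis that could not later count as a recurrence.** The entry wildcard allows it on paper, but 99.8% of matched patients have a PE code. A broad entry list beside a narrower outcome list is not an anomaly in itself.
- **That the repeated I80.3 proves a vena cava row was overwritten.** Its position is suggestive. However, R31.9 is also printed twice in the major bleeding list and I26.xx twice in the DVT inclusion line, with nothing evidently displaced.

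**Conclusion.** The printed primary-outcome definition differs between coding systems at two sites, the inferior vena cava and the remaining thoracic veins. This can be verified row by row. The mismatch bears only on admissions where one of these sites is the sole qualifying principal diagnosis.

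Under the assumed change date, the ICD-10 definition governs about two thirds to four fifths of the calendar windows. The number of events concerned cannot be derived from the documents. Even at an assumed 10% of events, pooled power moves only from 0.965 to 0.976, and the stated power is not shown to be wrong. Unequal loss between the arms is not shown either, because the documents do not report initiation dates by arm. The case for acting is a consistent primary-outcome definition, and rests on the printed list being the one that was run.

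**What to change.** Before the comparative analysis, whose report and date fields in Section 13 are still blank:

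1. Confirm which ICD-10 VTE list was run, and make the printed sheet match it.
2. Remove the duplicate I80.3 row.
3. Add the ICD-10 counterparts of 453.2.
4. For 453.87, either add its ICD-10 counterparts or delete it from the ICD-9 list, the only list where it appears. Deletion would remove any ICD-9 events at that site, so the net change in the count could go either way.
5. Rerun the overall outcome risk, not by arm, and update the expected events and power table in Section 10.

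The cost is a few rows in the code list, one rerun of the overall risk in each database and an updated table. No treatment comparison needs to be seen.

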# Appendix A

|                                             |                                                                                            |
|---------------------------------------------|--------------------------------------------------------------------------------------------|
| 453.9                                       | EMBOLISM AND THROMBOSIS OF UNSPECIFIED SITE                                                |
| ICD-10 Dx inpatient primary position |                                                                                            |
| PE                                   |                                                                                            |
| I26.0                                       | Pulmonary embolism with acute cor pulmonale                                                |
| I26.01                                      | Septic pulmonary embolism with acute cor pulmonale                                         |
| I26.02                                      | Saddle embolus of pulmonary artery with acute cor pulmonale                                |
| I26.09                                      | Other pulmonary embolism with acute cor pulmonale                                          |
| I26.9                                       | Pulmonary embolism without acute cor pulmonale                                             |
| I26.99                                      | Other pulmonary embolism without acute cor pulmonale                                       |
| DVT                                  |                                                                                            |
| I80.1                                       | Phlebitis and thrombophlebitis of femoral vein                                             |
| I80.10                                      | Phlebitis and thrombophlebitis of unspecified femoral vein                                 |
| I80.11                                      | Phlebitis and thrombophlebitis of right femoral vein                                       |
| I80.12                                      | Phlebitis and thrombophlebitis of left femoral vein                                        |
| I80.13                                      | Phlebitis and thrombophlebitis of femoral vein, bilateral                                  |
| I80.2                                       | Phlebitis and thrombophlebitis of other and unspecified deep vessels of lower extremities  |
| I80.20                                      | Phlebitis and thrombophlebitis of unspecified deep vessels of lower extremities            |
| I80.201                                     | Phlebitis and thrombophlebitis of unspecified deep vessels of right lower extremity        |
| I80.202                                     | Phlebitis and thrombophlebitis of unspecified deep vessels of left lower extremity         |
| I80.203                                     | Phlebitis and thrombophlebitis of unspecified deep vessels of lower extremities, bilateral |
| I80.209                                     | Phlebitis and thrombophlebitis of unspecified deep vessels of unspecified lower extremity  |
| I80.21                                      | Phlebitis and thrombophlebitis of iliac vein                                               |
| I80.211                                     | Phlebitis and thrombophlebitis of right iliac vein                                         |
| I80.212                                     | Phlebitis and thrombophlebitis of left iliac vein                                          |
| I80.213                                     | Phlebitis and thrombophlebitis of iliac vein, bilateral                                    |
| I80.219                                     | Phlebitis and thrombophlebitis of unspecified iliac vein                                   |
| I80.22                                      | Phlebitis and thrombophlebitis of popliteal vein                                           |
| I80.221                                     | Phlebitis and thrombophlebitis of right popliteal vein                                     |
| I80.222                                     | Phlebitis and thrombophlebitis of left popliteal vein                                      |
| I80.223                                     | Phlebitis and thrombophlebitis of popliteal vein, bilateral                                |
| I80.229                                     | Phlebitis and thrombophlebitis of unspecified popliteal vein                               |
| I80.23                                      | Phlebitis and thrombophlebitis of tibial vein                                              |
| I80.231                                     | Phlebitis and thrombophlebitis of right tibial vein                                        |

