| • Acute symptomatic PE with evidence of thrombosis demonstrated by imaging as follows:
- an intraluminal filling defect in segmental or more proximal branches on spiral computed tomography (CT) scan; or
- an intraluminal filling defect or a sudden cutoff of vessels more than 2.5 mm in diameter on the pulmonary angiogram; or
- a perfusion defect of at least 75% of a segment with a local normal ventilation result (high probability) on ventilation/perfusion lung scan (VPLS) | Measured 180 days prior to and including day of drug initiation in any diagnosis position and in an inpatient or ED care setting

Pulmonary embolism (PE):
ICD-9 Dx: 415.xx
ICD-10 Dx: I26.xx                                            |                                                                                                                                                                                                                                                                                  |                                                                                                                                                                                                                                                                                                                                                                                                                                                                                                                    |

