| - Gross hematuria                                           | 
Measured 1 day prior to and including the day of drug initiation in any diagnosis position in an inpatient or outpatient care setting
 
Gross hematuria:
 
ICD-9 Dx: 599.71 (not 599.7x)
ICD-10 Dx: R31.0
                                                                                                                                                                                                                                                                                                                                                                                                                                                                                                                                                                                      |  |  |
| - Evidence of poor healing of a major wound or major trauma | 
Measured 1 day prior and including the day of drug initiation in any diagnosis position in an inpatient or outpatient care setting
 
Non-healing surgical wound
 
ICD-9 Dx: 998.33
ICD-10 Dx: T81.33XA
                                                                                                                                                                                                                                                                                                                                                                                                                                                                                                                                                                                         |  |  |

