# Appendix A

|                                            |                                                                                       |
|--------------------------------------------|---------------------------------------------------------------------------------------|
| Title                               |                                                                                       |
| Venous Thromboembolism (VTE)               |                                                                                       |
| ICD-9 Dx inpatient primary position |                                                                                       |
| PE                                  |                                                                                       |
| 415.1                                      | PULMONARY EMBOLISM AND INFARCTION                                                     |
| 415.11                                     | IATROGENIC PULMONARY EMBOLISM AND INFARCTION                                          |
| 415.19                                     | OTHER PULMONARY EMBOLISM AND INFARCTION                                               |
| DVT                                 |                                                                                       |
| 451.1                                      | PHLEBITIS AND THROMBOPHLEBITIS OF DEEP VEINS OF LOWER EXTREMITIES                     |
| 451.11                                     | PHLEBITIS AND THROMBOPHLEBITIS OF FEMORAL VEIN (DEEP) (SUPERFICIAL)                   |
| 451.19                                     | PHLEBITIS AND THROMBOPHLEBITIS OF OTHER                                               |
| 451.2                                      | PHLEBITIS AND THROMBOPHLEBITIS OF LOWER EXTREMITIES UNSPECIFIED                       |
| 451.81                                     | PHLEBITIS AND THROMBOPHLEBITIS OF ILIAC VEIN                                          |
| 451.9                                      | PHLEBITIS AND THROMBOPHLEBITIS OF UNSPECIFIED SITE                                    |
| 453                                        | BUDD-CHIARI SYNDROME                                                                  |
| 453.1                                      | THROMBOPHLEBITIS MIGRANS                                                              |

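### The PE outcome list names septic and saddle PE only with acute cor pulmonale; unless I26.9 is matched as a prefix, recurrences under its other child codes are not counted, although the same codes qualify for entry

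*Combined protocol and SAP*

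**What the plan says.** **Entry.** The PE inclusion row of Appendix A uses wildcards: 415.xx for ICD-9 and "ICD-10 Dx: I26.xx". They apply in any diagnosis position, in inpatient or ED care, over the 180 days up to and including the index date.

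**Outcome.** Section 6.3.1 restricts the VTE outcome to hospital admissions with the diagnosis in principal position. The VTE sheet of Appendix A then lists the PE codes one by one:

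- ICD-9: 415.1, 415.11 and 415.19 ("OTHER PULMONARY EMBOLISM AND INFARCTION").
- ICD-10 with acute cor pulmonale: I26.0, I26.01 ("Septic pulmonary embolism with acute cor pulmonale"), I26.02 ("Saddle embolus of pulmonary artery with acute cor pulmonale") and I26.09 (other).
- ICD-10 without it: I26.9 ("Pulmonary embolism without acute cor pulmonale") and I26.99 ("Other pulmonary embolism without acute cor pulmonale").

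No rule states whether a listed header also matches its child codes. The opening rows of Appendix A refer to full ICD-10 lists in an external folder.

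**The concern.** The two halves of the ICD-10 list are not parallel. Septic and saddle emboli count as outcomes when cor pulmonale is recorded, so neither type is excluded in principle. Yet neither is named when it is absent, and no reason is given. The list is otherwise broad: it includes Budd-Chiari syndrome and chronic, distal and upper-extremity thrombosis.

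PE is central to this cohort. In the pooled PS-matched table of Appendix B, PE is recorded at baseline in 99.8% of warfarin and 99.9% of apixaban patients. A gap in the PE list would lower the sensitivity of the primary outcome and make index PE and recurrent PE inconsistent. The mortality component in Section 6.3.1 is inpatient death during a hospitalization for VTE. If that hospitalization is identified with the same list, a fatal admission coded in the gap would be lost too.

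**Working it through.** **1. What the list captures under each matching rule**

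| Code on a later inpatient principal diagnosis | Qualifies for entry (I26.xx) | Outcome, exact match | Outcome, prefix match |
|---|---|---|---|
| I26.01, I26.02, I26.09 | yes | yes | yes |
| I26.99 | yes | yes | yes |
| any other child of I26.9 | yes | **no** | yes, through I26.9 |

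The result depends entirely on the matching rule. ICD-9 has the same ambiguity: header 415.1, with 415.11 and 415.19 as the only listed children.

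**2. Which rule the documents point to**

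- Elsewhere Appendix A marks wildcards with an x. The gross hematuria row even sets the plain code 599.71 apart from 599.7x. The VTE outcome sheet contains no x.
- Headers and children are listed together throughout (I82.4, I82.40, I82.401). Under prefix matching the children would be redundant.
- Bare 453 is labelled Budd-Chiari syndrome and stands beside many other 453 rows. As a prefix it would absorb all of them and contradict its own label.
- 453.4 and 453.5 each appear twice, once for deep vessels and once for unspecified deep vessels. This looks like a header and a child written as separate codes.
- The numbering skips from 453.8 to 453.82, and from the I82.60 group to I82.62. Selecting codes in this way would have no effect if the headers 453.8 and I82.6 took in everything beneath them.

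Together these favour exact matching strongly. They do not prove it.

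**3. The plan's own figure**

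Inputs from the pooled table in Section 10: 7,140 matched patients (1:1), risk 13.74 per 1,000, HR 0.84, margin 1.8, two-sided alpha 0.05.

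- Events = 7,140 × 13.74 / 1,000 = 98.1036, as stated.
- Power = Φ( √(events × 0.25) × [ln 1.8 − ln 0.84] − 1.960 ) = Φ( 4.952 × 0.7621 − 1.960 ) = Φ(1.814) = 0.9652. The plan states 0.965194245, so it reproduces.

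**4. Direction and illustrative size**

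Section 9 reports the 13.74 per 1,000 as the overall risk of the primary outcome. It therefore presumably already reflects the list as implemented. If a share s of true events is now missed, the corrected count is 98.1036 / (1 − s). The documents give no value for s; those below are assumptions.

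| Assumed s | Events | Pooled power |
|---|---|---|
| 0 (as planned) | 98.1 | 0.965 |
| 2% | 98.1036 / 0.98 = 100.1 | 0.968 |
| 5% | 98.1036 / 0.95 = 103.3 | 0.972 |
| 10% | 98.1036 / 0.90 = 109.0 | 0.978 |

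**The case against.** The strongest reply is that nothing need be lost. I26.9 is on the list, and its label covers every PE without acute cor pulmonale. If the platform matches it as a prefix, coverage is complete. The external folder may also hold a fuller list. Both points stand, which is why the conclusion is conditional. A reader might infer from the printed sheet that septic and saddle recurrences without cor pulmonale are certainly missed. The documents do not establish that: they neither state the matching rule nor show the child codes in question. That such codes exist is inferred from the asymmetry with I26.0.

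A second reply is that entry and outcome are meant to differ. Entry is broad, while the outcome is confined to the inpatient principal position, and Appendix A cites a validation study of VTE codes beside the primary outcome. A narrower list is indeed not an error in itself. But restricting position and setting does not explain why two PE types count with cor pulmonale and are unnamed without it. If the list follows the cited study, the plan can say so.

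Two stronger readings also fail. A reader might infer that the gap pushes power below 0.965. It does not, because the event rate behind that figure was observed, so any undercount is presumably already in it. A reader might also infer a biased hazard ratio. The documents give no ground to expect the loss to differ between apixaban and warfarin.

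**Conclusion.** This is a minor point that is cheap to settle. As printed, and if codes are matched exactly, the outcome omits PE recurrences coded to any I26.9 child other than I26.99, while the same codes qualify a patient for entry. Exact matching is strongly indicated but not proven. The size of the loss cannot be derived from the documents. Under the assumed 2–10% loss, completing the list would raise expected events from 98.1 to about 100–109 and pooled power from 0.965 to about 0.968–0.978. This assumes that the 13.74 per 1,000 was obtained with the list as shown and that the assumed HR of 0.84 is unchanged. What is at stake is outcome sensitivity and agreement between the index and outcome definitions.

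**What to change.** Before the comparative analysis (Section 13 is still blank):

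1. Check the code list as implemented and state whether listed headers match their children.
2. Define the PE outcome as I26.xx (ICD-10) and 415.1x (ICD-9), keeping the inpatient principal position. 415.1x is the PE subset of the 415.xx used at entry, so the ICD-9 definitions would still not be identical. Alternatively, state why the remaining I26.9 children are excluded, for example because the list follows the cited validation study.
3. Re-run the event count and update Section 10.

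The cost is a two-line code-list edit and a re-run. If headers already match as prefixes, no result changes and the edit only makes the rule explicit.
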